We computed Bayes Factors (BFs) using the Savage-Dickey Density ratio (Wagenmakers et al., 2010) for all models where we set priors using the *hypothesis* function in *brms*. The Savage-Dickey Density ratio was calculated in the current context by dividing the posterior density by the prior density at zero (a null effect). Given that priors exert a large influence on the posterior estimates with small samples sizes, we used BFs to provide a sense of the influence of the priors on the study data rather than using them to provide a measure of confidence in the posterior estimates themselves as they are sometimes used (in *brms* if the *hypothesis* function is directional, it provides the latter estimate rather than the Savage-Dickey Density ratio). A BF equal to one means there is equal support for the null and alternative hypotheses while smaller BFs reflect greater support for the null and larger BFs reflect greater support for the alternative, with commonly accepted guidelines for the magnitude of the support (e.g., 1-3 is anecdotal evidence in favor of the alternative; 1/3-1 is anecdotal evidence in favor of the null).

For each result we report the beta estimates, 95% highest posterior density interval (HDI), and BFs of the model estimated with our original prior. We also provide the range of BFs as well as the sensitivity of the beta estimates based on our sensitivity analyses (see below).

Prior Estimates. We set informative priors based on expected effects that were based on a literature review of brief exposure-based intervention for social anxiety, as well as based on expert review. On a theoretical level, use of priors aligns with the idea that all available data should be used to draw inferences – including data from previous findings (Kruschke & Liddell, 2018). On a more practical level, there is substantial evidence to support the use of informative priors to address the ‘winner’s curse’ – which is where significant effects in an initial study are not subsequently replicated (Altoè et al., 2020). Moreover, Lemoine (2019)

conducted simulation analyses showing that weakly informative priors can regularize results in small samples ($n < 50$), providing a more conservative estimate.

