We largely followed the WAMBS (When to worry and how to Avoid the Misuse of Bayesian Statistics) checklist (Depaoli & van de Schoot, 2017). This checklist provides a step-by-step approach to ensuring that a model estimation procedure is acceptable and that the influence of the priors is well delineated. We tested the sensitivity of the priors by using less informative (smaller effects) parameter estimates as well as uninformative default (flat) priors centered on zero to determine the influence of different priors on the posterior estimates.

Priors for the effect of the intervention on fear of public speaking (PRPSA) were primarily based on a relatively recent study which also used a two-session public speaking exposure model (testing affect labeling as a potential mechanism; Niles et al., 2015). In terms of the efficacy of the augmentation for which there is no previous research, we used a prior that reflected a moderate effect ($\Delta 10$ on PRPSA score). It was impossible to predict whether there would be a greater gain at post-treatment followed by a ‘rebound’ (i.e., regression towards the mean) or whether the gains would continue and we tested the sensitivity of our priors by varying the magnitude of the effects as well as their direction (to a certain degree). We also tested a model with uninformative priors, centered on zero. Similarly, for the LSAS we used previous research to determine the priors. One challenge was that most studies addressing fear of public speaking did not have a clinical sample of socially anxious individuals – we predicted greater severity of social anxiety symptoms in the current study – and so drew from other studies as well (Lazarov et al., 2018). We primarily based our estimates of the efficacy of the intervention using a recently published single-session feasibility VRET study (Lindner et al., 2021). The estimate of the effect of the intervention provided a good starting place to inform our priors – based on the

likelihood that 2 sessions would be more potent, we also used estimates from other longer intervention studies.

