Priors on the effects of the intervention on proportions of fixations to audience members were not based on previously collected data because there is no literature that clearly delineates expected changes in gaze during public speaking challenges. We chose priors that reflected modest but meaningful effects, indicating changes in gaze behavior substantial enough to have potential implications for treatment outcomes as a causal mechanism. As with the other analyses, we tested several priors reflecting smaller effects as well as an uninformative prior centered on zero.

Power analysis. We did not conduct a power analysis that reflected the sample size for the current pilot study. We had initially conducted a power analysis through a simulation study prior to COVID-19, which indicated a sample size of 60 would be sufficient to detect a meaningful effect for both aims 1 and 2. However, due to COVID-19 enrollment ended before we could meet our recruitment goals. Given that research was necessarily stopped, we decided to rely on the strengths of the Bayesian approach highlighted above to investigate whether it would be worthwhile to conduct a more extensive RCT with a larger sample.

Data and syntax are available at <https://osf.io/un92m/>.

References

Bürkner, P. C. (2018). Advanced Bayesian multilevel modeling with the R package brms. *R Journal*. <https://doi.org/10.32614/rj-2018-017>

Depaoli, S., & van de Schoot, R. (2017). Improving transparency and replication in Bayesian statistics: The WAMBS-checklist. *Psychological Methods*. <https://doi.org/10.1037/met0000065>

Hayes, A. F., & Rockwood, N. J. (2017). Regression-based statistical mediation and moderation analysis in clinical research: Observations, recommendations, and implementation. *Behaviour Research and Therapy*. <https://doi.org/10.1016/j.brat.2016.11.001>

Kruschke, J. K., & Liddell, T. M. (2018). Bayesian data analysis for newcomers. *Psychonomic Bulletin and Review*. <https://doi.org/10.3758/s13423-017-1272-1>

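### Against a prior centred on benefit, a small Bayes factor is evidence only against the expected benefit and cannot separate no effect from harm; the SAP's formula and reading rule also run in opposite directions

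*SAP*

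**What the plan says.** The SAP's Data Analysis Plan computes Savage-Dickey Bayes factors for the models in which priors were set. It defines the ratio as "dividing the posterior density by the prior density at zero (a null effect", and then says that "smaller BFs reflect greater support for the null and larger BFs reflect greater support for the alternative". The labels attached are "1-3 is anecdotal evidence in favor of the alternative; 1/3-1 is anecdotal evidence in favor of the null". No margin for a meaningful difference is given.

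For the augmentation effect on PRPSA, the Prior Estimates section says "we used a prior that reflected a moderate effect ($\Delta 10$ on PRPSA score"). The spread and family of that prior are not stated. Sensitivity runs use smaller effects, some variation in direction, and flat priors centred on zero.

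The SAP disclaims the factors as a gauge of how far to trust the estimates: "we used BFs to provide a sense of the influence of the priors on the study data rather than using them to provide a measure". On output: "For each result we report the beta estimates, 95% highest posterior density interval (HDI), and BFs of the model estimated with our original prior". The range of factors and the sensitivity of the betas across priors are also promised. The Power analysis section says the Bayesian approach is relied on "to investigate whether it would be worthwhile to conduct a more extensive RCT with a larger sample". The protocol gives no rule for reading Bayes factors.

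**The concern.** A Savage-Dickey factor compares the exact value zero with whatever the prior expects. When the prior expects a benefit, data that contradict the benefit favour zero by comparison, and data pointing moderately towards harm can contradict it more strongly than data at zero. A reader applying the SAP's labels would then see stronger support for the null when guidance looks somewhat worse than when it makes no difference.

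The headline beta and HDI come from the same prior and are pulled the same way, so they do not fully correct that impression. What is at stake is the judgement on a larger trial: no added effect and possible worsening are different messages to carry forward from a small pilot.

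There is also a plain inconsistency. Posterior over prior density at zero is a ratio whose large values favour the null, yet the reading rule says that small values do.

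**Working it through.** **Inputs.** From the SAP: the 10-point prior effect, the null value of zero, and the labels at 1/3, 1 and 3. Assumed, because not stated: a normal prior with mean 10 (benefit positive) and SD t, and an estimate d with standard error s. The SAP gives no Bayes factor that could be reproduced.

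**Direction of the ratio.** Take s = t = 5 and d = 0. The posterior is normal with mean 5 and SD 3.54, so its density at zero is 0.0415. The prior density at zero is 0.0108. The SAP's formula gives 0.0415/0.0108 = 3.84. The SAP's reading rule would call that support for the alternative, although the data sit exactly on zero. The inverse, 0.26, is the quantity that the rule describes. Everything below uses that inverse, BF10 = prior density / posterior density at zero.

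**Where the factor is smallest.** BF10 = N(d; 10, s^2 + t^2) / N(d; 0, s^2), where the second argument is the mean and the third the variance. Setting the derivative of log BF10 to zero gives d/s^2 = (d - 10)/(s^2 + t^2), hence d = -10 x (s/t)^2. This is on the harm side for every t. At that d the posterior mean is exactly 0, so the headline beta also reads as no effect (95% interval +/-6.9 when s = t = 5).

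BF10 at s = 5:

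| Prior SD t | Minimum at d | d = +10 | d = 0 | d = -5 | d = -10 | d = -20 |
|---|---|---|---|---|---|---|
| 5 | -10 | 5.22 | 0.26 | 0.12 | 0.096 | 0.26 |
| 7.5 | -4.4 | 4.10 | 0.30 | 0.23 | 0.35 | 6.5 |
| 10 | -2.5 | 3.30 | 0.30 | 0.30 | 0.67 | 36 |
| 20 | -0.6 | 1.79 | 0.22 | 0.31 | 1.12 | 251 |

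A t prior with 3 degrees of freedom gives the same pattern: the minimum is at about -5 (scale 5) and -2.5 (scale 10). A normal(0, 10) prior at s = 5 gives 0.45 at d = 0 and 2.22 at both +10 and -10, so it treats the two directions alike.

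**How often.** Further assumptions: PRPSA SD 20, baseline-to-post correlation 0.5, equal arms. Then SE = 20 x sqrt(4/N) x sqrt(2 x (1 - 0.5)), which is 8.9, 6.3 and 5.2 at N = 20, 40 and 60. The final N is not stated; 60 is the SAP's pre-COVID figure and enrolment stopped short. At N = 40:

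| Prior SD t | BF10 < 1, true harm of 10 | BF10 < 1/3, true harm of 10 | BF10 < 1/3, true zero | Headline beta favours guidance, true harm of 10 |
|---|---|---|---|---|
| 5 | 99% | 93% | 46% | 83% |
| 7.5 | 95% | 58% | 38% | 32% |
| 10 | 79% | 14% | 18% | 17% |
| 20 | 61% | 22% | 51% | 8% |

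Under the same true harm the headline 95% interval lies wholly on the harm side in 0%, 2% and 9% of data sets for t = 5, 7.5 and 10. The flat-prior estimate has the harm sign in 94% (87% at N = 20, 97% at N = 60).

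**The case against.** A reader might infer that the plan will report harm as no effect. The documents do not support that. The SAP nowhere says that a small factor will be reported as no difference, or that the factor alone decides on a larger trial. It says the factors are there to show the influence of the priors. It promises a signed beta, an HDI and the betas under other priors, and a flat-prior beta is close to the plain data estimate. These objections stand, and they limit the point to how a small factor may be described.

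They do not remove it. Straight after disclaiming the factor as a measure of confidence, the SAP gives a scale of evidence for and against the null, and readers will use it. The headline beta shares the benefit prior. Smaller-benefit priors still sit on the benefit side, direction is varied only in part, and a truly flat prior yields no usable Savage-Dickey ratio. No proper zero-centred prior with a stated scale is described.

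A second tempting inference is that harm earns the null label more often than a true null does. For factors below 1/3 at N = 40 this holds at t = 5 and 7.5 but reverses at t = 10 and 20; at N = 60 it already reverses at t = 7.5 (48% against 52%). Many of the other factors below 1 fall between 1/3 and 1, which the SAP itself calls only anecdotal. The SAP points to public data and syntax, which may state the prior SDs; they were not available here.

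**Conclusion.** The point holds as a limit on interpretation. If the augmentation prior is normal and centred on the 10-point benefit, the smallest factor always falls at an estimate favouring control, so a small factor cannot distinguish no effect from harm. The size depends on s/t. With t at or below s the minimum lies 10 or more points into harm. With t = 20 and s = 5 it lies 0.6 points in, and a 20-point harm gives a very large factor. Centring on 10 is inferred from the SAP's wording. The prior SD, its family, the PRPSA SD, the correlation and the final N are assumptions, so the percentages illustrate a range and do not predict this trial's result.

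The conflict between the formula and the reading rule needs none of these assumptions; the two sentences must be reconciled.

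**What to change.** In the Bayes factor paragraph and the Prior Estimates section:

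1. State the direction of the factor so that formula and reading rule agree, and state the mean, SD and family of each prior.
2. Describe a small factor under the benefit-centred prior only as evidence against the expected benefit. Read support for the null only from a factor under a proper zero-centred prior, for example normal(0, 10) on PRPSA, which takes its scale from the SAP's own 10 points.
3. Beside the headline beta, HDI and factor, report the posterior probability that guidance is worse, under the zero-centred or flat prior. This is needed even after step 2: under normal(0, 10) about 40% of data sets with a true 10-point harm still give a factor below 1 at N = 40.
4. Do not state equivalence or no difference from a small factor.

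Do the same for LSAS on its own scale.

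A +/-10-point equivalence margin is not a good addition. It equals the SAP's whole moderate effect, and under the assumptions above the normal(0, 10) interval half-width, 1.96/sqrt(1/100 + 1/s^2), is 13.1 at N = 20 and 10.5 at N = 40. It could not be met there even with an observed difference of zero.

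**Cost.** One extra brms fit per outcome and a few sentences; no new data. The factor for a real benefit shrinks: at s = 6, an observed 10-point benefit gives 1.4 under normal(0, 10), against 3.1, 2.5 and 2.1 under the benefit-centred prior with t = 5, 7.5 and 10. More results will be reported as inconclusive.
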